#### 5.4.1 Avelumab

Every effort should be made to administer each of the investigational products at the planned dose and schedule. No avelumab dose modifications are permitted in this study, but the next administration of investigational product may be omitted based on persisting toxicity, as outlined in the next tables.

**Table 3.** Treatment Modification for Symptoms of Infusion-Related Reactions

NCI-CTCAE Grade	Treatment Modification for Avelumab
Grade 1 – mild Mild transient reaction; infusion interruption not indicated; intervention not indicated.	Decrease avelumab infusion rate by 50% and monitor closely for any worsening.
Grade 2 – moderate Therapy or infusion interruption indicated but responds promptly to symptomatic treatment (for example, antihistamines, NSAIDs, narcotics, IV fluids); prophylactic medications indicated for $\leq 24$ h.	Temporarily discontinue avelumab infusion. Resume infusion at 50% of previous rate once infusion-related reaction has resolved or decreased to at least Grade 1 in severity, and monitor closely for any worsening.
Grade 3 or Grade 4 – severe or life-threatening Grade 3: Prolonged (for example, not rapidly responsive to symptomatic medication and/or brief interruption of infusion); recurrence of symptoms following initial improvement; hospitalization indicated for clinical sequelae. Grade 4: Life-threatening consequences; urgent intervention indicated.	Stop avelumab infusion immediately and disconnect infusion tubing from the subject. Subjects have to be withdrawn immediately from study drug treatment and must not receive any further study drug treatment.

 
-If avelumab infusion rate has been decreased by 50% or interrupted due to an infusion reaction, it must remain decreased for the next scheduled infusion. If no infusion reaction is observed in the next scheduled infusion, the infusion rate may be returned to baseline at the subsequent infusions based on investigator's medical judgment.
 
- If hypersensitivity reaction occurs, the subject must be treated according to the best available medical practice.
 
	

IV = intravenous; NCI-CTCAE = National Cancer Institute-Common Terminology Criteria for Adverse Event; NSAIDs = nonsteroidal anti-inflammatory drugs.

Table 4. Management of Immune-mediated Adverse Reactions

Gastrointestinal irAEs		
Severity of Diarrhea/Colitis (NCI-CTCAE v4.03)	Initial Management	Follow-up Management
Grade 1 Diarrhea: < 4 stools/day over Baseline Colitis: asymptomatic	Continue avelumab therapy Symptomatic treatment (e.g. loperamide)	Close monitoring for worsening symptoms Educate subject to report worsening immediately If worsens: Treat as Grade 2, 3 or 4.
Grade 2 Diarrhea: 4 to 6 stools per day over Baseline; IV fluids indicated < 24 hours; not interfering with ADL Colitis: abdominal pain; blood in stool	Withhold avelumab therapy Symptomatic treatment	If improves to Grade $\leq$ 1: Resume avelumab therapy  If persists > 5-7 days or recurs: Treat as Grade 3 or 4.
Grade 3 to 4 Diarrhea (Grade 3): $\geq$ 7 stools per day over Baseline; incontinence; IV fluids $\geq$ 24 h; interfering with ADL Colitis (Grade 3): severe abdominal pain, medical intervention indicated, peritoneal signs Grade 4: life-threatening, perforation	Withhold avelumab for Grade 3. Permanently discontinue avelumab for Grade 4 or recurrent Grade 3.  1.0 to 2.0 mg/kg/day prednisone IV or equivalent Add prophylactic antibiotics for opportunistic infections Consider lower endoscopy	If improves: Continue steroids until Grade $\leq$ 1, then taper over at least 1 month; resume avelumab therapy following steroids taper (for initial Grade 3).  If worsens, persists > 3 to 5 days, or recurs after improvement: Add infliximab 5mg/kg (if no contraindication). Note: infliximab should not be used in cases of perforation or sepsis.

Dermatological irAEs		
Grade of Rash (NCI-CTCAE v4.03)	Initial Management	Follow-up Management
Grade 1 to 2 Covering $\leq$ 30% body surface area	Continue avelumab therapy Symptomatic therapy (for example, antihistamines, topical steroids)	If persists $>$ 1 to 2 weeks or recurs: Withhold avelumab therapy Consider skin biopsy  Consider 0.5-1.0 mg/kg/day prednisone or equivalent. Once improving, taper steroids over at least 1 month, consider prophylactic antibiotics for opportunistic infections, and resume avelumab therapy following steroids taper. If worsens: Treat as Grade 3 to 4.
Grade 3 to 4 Grade 3: Covering $>$ 30% body surface area; Grade 4: Life threatening consequences	Withhold avelumab for Grade 3. Permanently discontinue for Grade 4 or recurrent Grade 3. Consider skin biopsy Dermatology consult 1.0 to 2.0 mg/kg/day prednisone or equivalent Add prophylactic antibiotics for opportunistic infections	If improves to Grade $\leq$ 1: Taper steroids over at least 1 month; resume avelumab therapy following steroids taper (for initial Grade 3).
Pulmonary irAEs		
Grade of Pneumonitis (NCI-CTCAE v4.03)	Initial Management	Follow-up Management
Grade 1 Radiographic changes only	Consider withholding avelumab therapy Monitor for symptoms every 2 to 3 days	Re-assess at least every 3 weeks If worsens: Treat as Grade 2 or Grade 3 to 4.

	Consider Pulmonary and Infectious Disease consults	
Grade 2 Mild to moderate new symptoms	Withhold avelumab therapy Pulmonary and Infectious Disease consults Monitor symptoms daily; consider hospitalization 1.0 to 2.0 mg/kg/day prednisone or equivalent Add prophylactic antibiotics for opportunistic infections Consider bronchoscopy, lung biopsy	Re-assess every 1 to 3 days If improves: When symptoms return to Grade $\leq$ 1, taper steroids over at least 1 month, and then resume avelumab therapy following steroids taper If not improving after 2 weeks or worsening: Treat as Grade 3 to 4.
Grade 3 to 4 Grade 3: Severe new symptoms; New/worsening hypoxia; Grade 4: Life-threatening	Permanently discontinue avelumab therapy. Hospitalize. Pulmonary and Infectious Disease consults. 1.0 to 2.0 mg/kg/day prednisone or equivalent Add prophylactic antibiotics for opportunistic infections Consider bronchoscopy, lung biopsy	If improves to Grade $\leq$ 1: Taper steroids over at least 1 month If not improving after 48 hours or worsening: Add additional immunosuppression (for example, infliximab, cyclophosphamide, IV immunoglobulin, or mycophenolate mofetil)
Hepatic irAEs		
Grade of Liver Test Elevation (NCI-CTCAE v4.03)	Initial Management	Follow-up Management
Grade 1 Grade 1 AST or ALT $>$ ULN to 3.0 $\times$ ULN and/or Total bilirubin $>$ ULN to 1.5 $\times$ ULN	Continue avelumab therapy	Continue liver function monitoring If worsens: Treat as Grade 2 or 3 to 4.
Grade 2	Withhold avelumab therapy	If returns to Grade $\leq$ 1:

AST or ALT > 3.0 to $\leq$ 5 x ULN and/or total bilirubin > 1.5 to $\leq$ 3 x ULN	Increase frequency of monitoring to every 3 days.	Resume routine monitoring; resume avelumab therapy. If elevation persists > 5 to 7 days or worsens: Treat as Grade 3 to 4.
Grade 3 to 4 AST or ALT > 5 x ULN and/or total bilirubin > 3 x ULN	Permanently discontinue avelumab therapy Increase frequency of monitoring to every 1 to 2 days 1.0 to 2.0 mg/kg/day prednisone or equivalent Add prophylactic antibiotics for opportunistic infections Consult gastroenterologist/hepatologist Consider obtaining MRI/CT scan of liver and liver biopsy if clinically warranted	If returns to Grade $\leq$ 1: Taper steroids over at least 1 month If does not improve in > 3 to 5 days, worsens or rebounds: Add mycophenolate mofetil 1 gram (g) twice daily If no response within an additional 3 to 5 days, consider other immunosuppressants per local guidelines.
Renal irAEs		
Grade of Creatinine Increased (NCI-CTCAE v4.03)	Initial Management	Follow-up Management
Grade 1 Creatinine increased > ULN to 1.5 x ULN	Continue avelumab therapy	Continue renal function monitoring If worsens: Treat as Grade 2 to 3 or 4.
Grade 2 to 3 Creatinine increased > 1.5 and $\leq$ 6 x ULN	Withhold avelumab therapy Increase frequency of monitoring to every 3 days 1.0 to 2.0 mg/kg/day prednisone or equivalent. Add prophylactic antibiotics for opportunistic infections Consider renal biopsy	If returns to Grade $\leq$ 1: Taper steroids over at least 1 month, and resume avelumab therapy following steroids taper. If worsens: Treat as Grade 4.

Grade 4 Creatinine increased > 6 x ULN
	
Permanently discontinue avelumab therapy Monitor creatinine daily 1.0 to 2.0 mg/kg/day prednisone or equivalent. Add prophylactic antibiotics for opportunistic infections Consider renal biopsy Nephrology consult
	
If returns to Grade ≤1: Taper steroids over at least 1 month.

Cardiac irAEs		
Myocarditis	Initial Management	Follow-up Management

New onset of cardiac signs or symptoms and / or new laboratory cardiac biomarker elevations (e.g. troponin, CK-MB, BNP) or cardiac imaging abnormalities suggestive of myocarditis.
	
Withhold avelumab therapy. Hospitalize.  In the presence of life threatening cardiac decompensation, consider transfer to a facility experienced in advanced heart failure and arrhythmia management.  Cardiology consult to establish etiology and rule-out immune-mediated myocarditis.  Guideline based supportive treatment as per cardiology consult.*  Consider myocardial biopsy if recommended per cardiology consult.
	
If symptoms improve and immune-mediated etiology is ruled out, re-start avelumab therapy.  If symptoms do not improve/worsen, viral myocarditis is excluded, and immune-mediated etiology is suspected or confirmed following cardiology consult, manage as immune-mediated myocarditis.

Immune-mediated myocarditis
	
Permanently discontinue avelumab. Guideline based supportive treatment as appropriate as per cardiology consult.*
	
Once improving, taper steroids over at least 1 month.  If no improvement or worsening, consider additional

	
1.0 to 2.0 mg/kg/day prednisone or equivalent Add prophylactic antibiotics for opportunistic infections.
	immunosuppressants (e.g. azathioprine, cyclosporine A).

*Local guidelines, or e.g. ESC or AHA guidelines ESC guidelines website: https://www.escardio.org/Guidelines/Clinical-Practice-Guidelines AHA guidelines website: http://professional.heart.org/professional/GuidelinesStatements/searchresults.jsp?q=&y=&t=1001
		
Endocrine irAEs		
Endocrine Disorder	Initial Management	Follow-up Management
Grade 1 or Grade 2 endocrinopathies (hypothyroidism, hyperthyroidism, adrenal insufficiency, type I diabetes mellitus)	
Continue avelumab therapy Endocrinology consult if needed
 
Start thyroid hormone replacement therapy (for hypothyroidism), anti-thyroid treatment (for hyperthyroidism), corticosteroids (for adrenal insufficiency) or insulin (for Type I diabetes mellitus) as appropriate.
 
Rule-out secondary endocrinopathies (i.e. hypopituitarism / hypophysitis)
	Continue hormone replacement/suppression and monitoring of endocrine function as appropriate.
Grade 3 or Grade 4 endocrinopathies (hypothyroidism, hyperthyroidism, adrenal insufficiency, type I diabetes mellitus)	
Withhold avelumab therapy Consider hospitalization Endocrinology consult
 
Start thyroid hormone replacement therapy (for hypothyroidism), anti-thyroid treatment (for hyperthyroidism), corticosteroids (for adrenal insufficiency) or insulin (for type I diabetes mellitus) as appropriate.
	
Resume avelumab once symptoms and/or laboratory tests improve to Grade <math>\leq 1</math> (with or without hormone replacement/suppression).
 
Continue hormone replacement/suppression and monitoring of endocrine function as appropriate.

	Rule-out secondary endocrinopathies (i.e. hypopituitarism / hypophysitis)	
Hypopituitarism/Hypophysitis (secondary endocrinopathies)	
If secondary thyroid and/or adrenal insufficiency is confirmed (i.e. subnormal serum FT4 with inappropriately low TSH and/or low serum cortisol with inappropriately low ACTH) :
 
 
• Refer to endocrinologist for dynamic testing as indicated and measurement of other hormones (FSH, LH, GH/IGF-1, PRL, testosterone in men, estrogens in women)
 
• Hormone replacement/suppressive therapy as appropriate
 
• Perform pituitary MRI and visual field examination as indicated
 
 
If hypophysitis confirmed:
 
 
• Continue avelumab if mild symptoms with normal MRI. Repeat the MRI in 1 month
 
• Withhold avelumab if moderate, severe or life-threatening symptoms of hypophysitis and/or abnormal MRI. Consider hospitalization. Initiate corticosteroids (1 to 2 mg/kg/day prednisone or equivalent) followed by corticosteroids taper during at least 1 month.
 
• Add prophylactic antibiotics for opportunistic infections.
 
	
Resume avelumab once symptoms and hormone tests improve to Grade <math>\leq 1</math> (with or without hormone replacement).
 
In addition, for hypophysitis with abnormal MRI, resume avelumab only once shrinkage of the pituitary gland on MRI/CT scan is documented.
 
Continue hormone replacement/suppression therapy as appropriate.

Other irAEs (not described above)		
Grade of other irAEs (NCI-CTCAE v4.03)	Initial Management	Follow-up Management
Grade 2 or Grade 3 clinical signs or symptoms suggestive of a potential irAE	Withhold avelumab therapy pending clinical investigation	If irAE is ruled out, manage as appropriate according to the diagnosis and consider restarting avelumab therapy If irAE is confirmed, treat as Grade 2 or 3 irAE.
Grade 2 irAE or first occurrence of Grade 3 irAE	Withhold avelumab therapy 1.0 to 2.0 mg/kg/day prednisone or equivalent Add prophylactic antibiotics for opportunistic infections Specialty consult as appropriate	If improves to Grade $\leq$ 1: Taper steroids over at least 1 month and resume avelumab therapy following steroids taper.
Recurrence of same Grade 3 irAEs	Permanently discontinue avelumab therapy 1.0 to 2.0 mg/kg/day prednisone or equivalent Add prophylactic antibiotics for opportunistic infections Specialty consult as appropriate	If improves to Grade $\leq$ 1: Taper steroids over at least 1 month.
Grade 4	Permanently discontinue avelumab therapy 1.0 to 2.0 mg/kg/day prednisone or equivalent and/or other immunosuppressant as needed Add prophylactic antibiotics for opportunistic infections Specialty consult.	If improves to Grade $\leq$ 1: Taper steroids over at least 1 month
Requirement for 10 mg per day or greater prednisone or equivalent for more than 12 weeks for reasons other than hormonal replacement for adrenal insufficiency	Permanently discontinue avelumab therapy Specialty consult	

Persistent Grade 2 or 3 irAE lasting 12 weeks or longer		
--	--	--

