## 4. Study Population

### 4.1 Inclusion criteria

Subjects must meet all the following criteria:

1. Male or female subjects aged  $\geq$  18 years
2. Eastern Cooperative Oncology Group ECOG performance status 0 or 1
3. Histologically confirmed recurrent or metastatic adenoid cystic carcinoma not amenable to curative intent surgery or radiotherapy
4. Measurable disease per RECIST 1.1
5. Evidence of disease progression within 6 months of study enrollment
6. Previously untreated subjects and subject treated with any number of prior lines of therapy are eligible
7. Adequate physiologic function defined as: Hematologic: Absolute neutrophil count (ANC)  $\geq$  1.5  $\times$  10^9/L, platelet count  $\geq$  100  $\times$  10^9/L, and hemoglobin  $\geq$  9 g/dL (may have been transfused). Hepatic: Total bilirubin level  $\leq$  1.5  $\times$  the upper limit of normal (ULN) range and AST and ALT levels  $\leq$  2.5  $\times$  ULN or AST and ALT levels  $\leq$  5  $\times$  ULN (for subjects with documented metastatic disease to the liver). Renal: Estimated creatinine clearance  $\geq$  30 mL/min according to the Cockcroft-Gault formula (or local institutional standard method)
8. Must have archival tissue (Formalin-Fixed, Paraffin-Embedded (FFPE) tissue available-minimum of 15 unstained slides) or be willing to undergo a biopsy
9. For patients receiving antitherapeutic coagulation, patients must be on stable anticoagulant regimen and INR or aPTT must be  $\leq$  1.5 upper limit of normal.
10. Females of childbearing potential must not be breast feeding and must have a negative serum or urine pregnancy test and must agree to use highly effective contraception for a minimum of two weeks prior to receiving study medication until 30 days after discontinuation of the study medication. Acceptable methods of contraception include total and true sexual abstinence, hormonal contraceptives that are not prone to drug-drug interactions (IUS Levonorgestrel Intra Uterine System (Mirena), Medroxyprogesterone injections (Depo-Provera)), copper-banded intra-uterine devices,

and vasectomized partner. All hormonal methods of contraception should be used in combination with the use of a condom by their sexual male partner.

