## Proprietary of MD Anderson Cancer Center

axitinib since single agent activity has been reported with this agent in ACC. Guidance for management of the most common overlapping adverse events are outlined below:

- Diarrhea:

Grade 1-2: manage with anti-diarrheal agents (E.g., loperamide). If no improvement dose-reduce/hold axitinib first, if no improvement hold avelumab (management as per Table 4), if improvement, axitinib can be re-started.

Grade  $\geq 3$ : hold both drugs, discard an infectious agent, and treat with anti-diarrheal agents and steroids as per Table 4. Re-start with single agent axitinib.

- Fatigue:

Grade  $\geq 2$ : Hold avelumab first, if no improvement dose-reduce axitinib, if improvement avelumab can be re-started. If only single agent can be tolerated, prioritize axitinib.

- Hypertension

- Hold Axitinib when unable to control blood pressure to  $<140/90$  on greater than 4 Blood pressure medications from multiple classes on maximally tolerated doses.
- Qtc-Hold for  $Qtc > 500$ msec, for  $Qtc$  from 470-499msec, Cardiology collaborator will evaluate and review for drug interactions and presence of underlying structural heart disease, and resume when  $Qtc$  by EKG interpretation shows normal  $Qtc$

- Transaminitis (increase in ALT and/or AST):

Grade 1-2: Hold avelumab first, if no improvement, dose-reduce/discontinue axitinib, if improvement avelumab can be re-started

Grade  $\geq 3$ : hold both drugs, discard an infectious agent, and treat with steroids as per Table 4. Re-start with single agent axitinib.

Other overlapping AEs:

- Decreased appetite, nausea, weight loss, vomiting, dyspnea, arthralgia, stomatitis are more common with axitinib, therefore, dose reductions of these agent should precede avelumab hold.
- Rash, hypothyroidism, asthenia and hematologic toxicities should be initially attributed to avelumab and managed accordingly (Tables 3 and 4), if no improvement by avelumab hold, axitinib dose-reduction/discontinuation should follow.

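### Table 4's hepatic Grade 2 and renal Grade 2 to 3 rows accept recovery only at Grade 1 or lower, which some eligible patients exceed at entry; adding return to baseline is a minor, cheap improvement

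*Combined protocol and SAP*

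**What the plan says.** **Entry.** Inclusion criterion 7 (Section 4.1) caps AST and ALT at 2.5 × ULN, raised to 5 × ULN "for subjects with documented metastatic disease to the liver". Bilirubin is capped at 1.5 × ULN. Renal function is set by a clearance of at least 30 mL/min, "according to the Cockcroft-Gault formula (or local institutional standard method"), with no cap on serum creatinine.

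**Hepatic management.** Table 4 in Section 5.4.1 works by "Grade of Liver Test Elevation (NCI-CTCAE v4.03"), in multiples of ULN. Grade 1 ends at 3.0 × ULN for AST/ALT, and Grade 2 runs from there to 5 × ULN. At Grade 2 avelumab is withheld. Only at Grade 1 or lower does the row say "Resume routine monitoring; resume avelumab therapy". Otherwise: "If elevation persists > 5 to 7 days or worsens: Treat as Grade 3 to 4". The Grade 3 to 4 row is permanent discontinuation with prednisone 1 to 2 mg/kg/day.

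**Renal management.** Grade 1 ends at creatinine 1.5 × ULN. The Grade 2 to 3 row (up to 6 × ULN) withholds avelumab and starts prednisone 1 to 2 mg/kg/day. On return to Grade 1 or lower: "Taper steroids over at least 1 month, and resume avelumab therapy following steroids taper".

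**The neighbouring rule.** Section 5.4 lists transaminitis among toxicities that either drug could cause and says: "Grade 1-2: Hold avelumab first, if no improvement, dose-reduce/discontinue axitinib, if improvement avelumab can be re-started". It gives no target level. It has no creatinine rule.

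**The concern.** The recovery thresholds in these two rows are lower than values at which the protocol allows a first dose. A patient who enters above the threshold, has a genuine rise and then settles back to the entry value has recovered in any ordinary sense, but not by the row.

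In the hepatic row the result, read literally, is permanent loss of avelumab and high-dose steroid for a patient back where he or she started. In the renal row it is steroid treatment with no written start to the taper and no written return to avelumab. Other rules differ: the diarrhea row in the same table counts stools relative to baseline, and Section 5.4.2 lets axitinib restart at Grade 2 or lower. What is at stake is the treatment of a few individuals, not the trial's inference.

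**Working it through.** The plan states no figure on this point to reproduce. The check sets the entry limits against the recovery thresholds, then asks how many patients could be affected.

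**1. Where the overlap lies**

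| Measure | Highest permitted entry value | Recovery threshold (top of Grade 1) | Overlap |
|---|---|---|---|
| AST/ALT, no liver metastases | 2.5 × ULN | 3.0 × ULN | none |
| AST/ALT, liver metastases | 5 × ULN | 3.0 × ULN | above 3.0, up to 5 × ULN |
| Bilirubin | 1.5 × ULN | 1.5 × ULN | none |
| Creatinine | no cap; clearance ≥ 30 mL/min | 1.5 × ULN | possible, see step 3 |

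**2. Hepatic gap.** Fall below entry needed to count as recovered = 1 − 3.0/entry:
- entry 3.5 × ULN: 14.3%
- entry 4.0 × ULN: 25.0%
- entry 5.0 × ULN: 40.0%

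Example: entry 4.0, rise to 4.5, back to 4.0 × ULN. Every value is Grade 2, so the row's recovery test is never met and the 5 to 7 day step applies.

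**3. Renal gap.** Inverting Cockcroft-Gault at clearance 30 mL/min: creatinine = (140 − age) × weight / (72 × 30), times 0.85 for women. The documents give no creatinine ULN; 1.2–1.3 mg/dL (men) and 1.0–1.1 mg/dL (women) are assumed.
- Man, 60 years, 70 kg: 80 × 70 / 2160 = 2.59 mg/dL. The threshold is 1.80 to 1.95 mg/dL, so a fall of 30.6% to 24.8% is needed.
- Woman, 60 years, 65 kg: 80 × 65 × 0.85 / 2160 = 2.05 mg/dL. The threshold is 1.50 to 1.65 mg/dL, so a fall of 26.7% to 19.4% is needed.

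Over ages 40–80 and weights 50–100 kg, creatinine at the clearance floor runs from about 1.1 to 3.9 × ULN. Some older or lighter patients are therefore not affected. An 80-year-old man of 60 kg, for instance, has 1.67 mg/dL, or 1.28–1.39 × ULN. This shows that the overlap is possible, not how often it occurs.

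**4. Expected hepatic number.** Assumptions not in the documents: 10–30% of the 30 patients have liver metastases, and 5–20% of those enter above 3 × ULN.
- Patients in the overlap: 30 × 0.10 × 0.05 = 0.15, to 30 × 0.30 × 0.20 = 1.8.
- A worsening is also needed. Table 2 (Section 1.4) gives treatment-related ALT increase in 16/55 = 0.291, assumed to carry over from kidney cancer: 0.15 × 0.291 = 0.044, to 1.8 × 0.291 = 0.524.
- With the AST rate, 14/55 = 0.255: 0.038 to 0.458.
- If every patient in the overlap worsened: at most 1.8.

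These counts make no deduction for cases that Section 5.4 would govern.

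**5. Renal scale.** Section 1.2.1 reports immune-related nephritis or renal dysfunction in 0.1% on single-agent avelumab: 30 × 0.001 = 0.03 cases, before requiring a raised entry creatinine. Non-immune rises could also fall into the row, so this is not an upper bound.

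**The case against.** The strongest reply is Section 5.4. It has its own Grade 1–2 transaminitis rule, restarts avelumab on improvement without a Grade 1 target or a 5 to 7 day clock, and refers to Table 4 for transaminitis only at Grade 3 or above. Every patient starts on both drugs, so most rises in AST/ALT could be put under it. This largely stands: it may govern most hepatic cases. It does not remove the gap, because it covers only toxicity that either drug could cause, names no level, and the documents do not say which rule prevails. It offers nothing for creatinine.

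Three further replies carry some weight:
- The persistence step could be read as meaning the new elevation only. Section 7.2.1 follows serious adverse events until laboratory values are back at baseline, which fits that reading. But it is a follow-up rule, not a restart rule, and the row itself grades by ULN multiple.
- Exclusion criterion 17 lets the investigator keep out patients whose laboratory abnormalities raise risk. Inclusion criterion 7 nevertheless accepts these values expressly.
- An absolute threshold is a defensible caution after an on-treatment liver event; Section 1.2.1 reports two fatal immune-related hepatitis cases. Keeping the absolute stops meets most of this.

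A reader might also infer that an unchanged entry value already triggers withholding and steroids. The documents do not support that. Section 5.4.1 says "the next administration of investigational product may be omitted based on persisting toxicity, as outlined in the next tables", Table 4's headings concern immune-related events, and Section 7.1.1 does not count a pre-existing condition as an adverse event unless it worsens.

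**Conclusion.** The point holds as a minor wording defect in two Table 4 rows. It needs three things together: an eligible entry value above Grade 1, a real worsening, and a return to the entry value. Well under one patient is expected: about 0.04 to 0.5 on the hepatic side, under assumed frequencies of liver metastases and raised entry values, and fewer still if Section 5.4 is followed. The renal overlap is shown to be possible under an assumed ULN; its frequency is unknown.

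Two stronger readings are tempting and not supported:
- **That renal patients are led to permanent discontinuation.** The renal Grade 2 to 3 row has no persistence step. The 12-week steroid limit sits under immune-related events not described elsewhere in the table, so its use here is uncertain.
- **That the trial's results are affected.** Section 9.1 keeps all eligible enrolled patients in the efficacy analyses, Section 5.9 lets a patient continue the other drug, and no effect on the primary response analysis is shown.

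**What to change.** In the hepatic Grade 2 and renal Grade 2 to 3 rows of Table 4, replace *returns to Grade ≤ 1* with *returns to Grade ≤ 1, or to baseline if baseline was above Grade 1*. Define baseline as the last value before the first avelumab dose. Let the hepatic 5 to 7 day step refer to elevation above that level. The patient who goes from 4.0 to 4.5 and back to 4.0 × ULN would then count as recovered and could resume.

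Keep the absolute stops for AST/ALT above 5 × ULN and creatinine above 6 × ULN for everyone. A patient entering near 5 × ULN still has little room before the stop; that is an acceptable safety limit. No new worsening threshold is needed.

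The cost is a few words in two rows. Section 5.3 already requires chemistry at screening and before each avelumab dose. The downside is that, in these few patients, avelumab may resume at a raised value, though one the protocol accepted for the first dose. The change does not settle whether Section 5.4 or Table 4 prevails where they differ; that needs a separate decision.
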